Title of Study: Alternating Urine Redox Status of Consecutive Menstrual Cycles [Uro-001]

Sponsor: Urobiologics LLC, [name]

Date of Final Protocol: October 16, 2019

Approved by:

For the Sponsor:

[Signature on File]

10/16/19

[name]
President, Urobiologics, LLC

Principal Investigator:

[Signature on File]

10/16/19

[name], PhD
Associate Research Scientist, Department of Epidemiology
University of Michigan School of Public Health

Title of study:

Alternating Urine Redox Status of Consecutive Menstrual Cycles [Uro-001]

Name of Sponsor:

UROBIOLOGICS, LLC

Population:

40 Female subjects

Estimated duration of study:

November 2019 – October 2020

Objective:

The Sponsor believes there is variability in the relative redox status in women's urine across menstrual cycles. This validation study will involve the collection and analysis of urine samples from non-pregnant women to determine the existence of alternating redox status between two consecutive menstrual cycles. If the hypothesis is proved, future research could examine if there are related fertility issues.

Study design synopsis:

Approximately 40 women with normal reported menstrual cycles will be included in this validation study.

All subjects will receive an explanation of the study and what is asked of them. They will sign informed consent and then undergo screening for study eligibility. If subjects fail the screening evaluation for reasons related to incidental transitory conditions yet wish to participate, they may subsequently be re-screened again after providing informed consent.

Subjects who meet the entry criteria (along with providing informed consent) will receive written instructions for participation in the study; an information sheet for logging their period dates, tracking medications and fevers, and instructions for returning the samples; and all supplies needed for collecting the urine samples (collection kits).

Subjects will collect urine over two days at the mid-point of their menstrual cycles (see Appendix 1) until three separate pairs of two consecutive cycles are obtained (requiring a minimum of 6 months of participation in the study). Subjects may receive telephone calls, texts, or other reminders to obtain the urine, as long as the reminder method is acceptable to the subject.

Urine specimens will be delivered to the University of Michigan CLASS Laboratory or to a second location for transfer to the CLASS Laboratory; if necessary, specimens may be sent through postal or carrier services. In the CLASS Laboratory, aliquots of urine will be drawn from the specimens, randomized and blinded in consecutive cycle pairs, and sent to Urobiologics for analysis. Urobiologics will send the reports of results to the CLASS Laboratory.

When all samples have been collected and analyzed, the blind will be broken, the data coded into spreadsheets, and statistical analysis will be performed. The principal hypothesis is that women have menstrual cycles that alternate between opposite redox states.

Inclusion/Exclusion Criteria:

Inclusion criteria:

1. Female subject, between the years 18-30, at the time of consent.
2. Subject reports “regular” menstrual cycles (i.e., cycle is 25 to 35 days and subject can typically predict onset of menses within ± 3 days).
3. Subject may be sexually abstinent or sexually active; if sexually active, she should be trying to prevent pregnancy using non-hormonal methods such as condoms.
4. Subject is willing to participate and is capable of giving informed consent. (Note: Consent must be obtained prior to any study-related procedures.)
5. Subject must be willing to comply with all study procedures.
6. Subject agrees to avoid alcohol, unapproved medications (prescription, OTC, or other), marijuana products, and illicit substances for 3 days prior to each urine collection. If medications must be taken, the collection will be discarded and another opportunity offered.

Exclusion criteria:

1. Subject is pregnant, or trying to or planning to become pregnant during the study.
2. Subject was pregnant within 1 year of beginning study, regardless of the outcome of pregnancy.
3. Subject who is breastfeeding.
4. Subject who is not menstruating for any reason or plans to undergo or change circumstances that might affect menstruation (e.g., certain athletic training regimens, significant dietary changes).
5. History of recent or current irregular menstrual cycles (as self-reported by the subject).
6. Subject reports she has been told by a medical professional that she is not ovulating (i.e., has anovulatory periods) at any time during the previous 12 months.
7. Subject is using or planning to use any method to regulate her periods.
8. Subject smokes (includes tobacco and marijuana) or vapes.
9. By history, subject has medical problems that might influence the results of the study, such as endocrinologic, renal, or hormonal problems.
10. Known polycystic ovarian syndrome (by history).
11. Subject is taking or planning to take hormones or hormone- enhancing/manipulating pharmaceuticals (including “morning after pill” [levonorgestrel], birth control pills, Clomid [clomiphene citrate], Femara [letrozole], Cialis [tadalafil]*, Viagra [sildenafil]* and similar medications) and/or agents to influence hormonal status such as herbal products or nutritional supplements. (*Not approved for use and should be avoided by women.)
12. Subject is using or planning to use hormonal contraceptives of any type, including oral contraceptives and intrauterine devices.
13. Subject is using or planning to use hormonal therapies for acne vulgaris or other conditions, including spironolactone, flutamide, metformin, or oral contraceptives used as acne therapies, including Ortho Tri-Cyclen (combination of norgestimate and ethinyl estradiol [EE]), Estrostep (combination of norethindrone acetate and EE), and Yaz/Yasmin (combination of drospirenone and EE).

CONFIDENTIAL

14. Subject is using or planning to use estrogen products, including topicals/creams, for any purpose.
15. Subject is using or planning to use androgens or anabolic steroids (e.g., stanazolol/danazol) for any reason, including for training or athletic purposes..
16. Subject has attempted or taken IVF or IUI treatment within the prior six months.
17. Subject has uncontrolled diabetes or other significant medical disorder that might, in the investigator's opinion, preclude completion of the study or suggest that an exclusion criterion will ensue.
18. Subject reports difficulty handling biologic fluids, specifically urine, or gives other reasons why she is hesitant to participate.

Methods for subjects to collect urine samples:

See Appendix 1 for instructions to subjects and methodology.

Delivery of samples to UM research laboratory:

See Appendix 1.

Processing of samples in UM research laboratory:

Preparation of samples:

1. Upon receipt of the sample collection kit from each subject, check to ensure that the bag label has been transferred to the Sample Collection Form. Verify that the urine barcode numbers listed on the sample sheet match the numbers on the urine vial. Assure that two separate 30 mL vials are present from the same subject, one labeled "A" or "#1" and one labeled "B" or "#2", AND that they contain dates consistent with being obtained during two consecutive menstrual cycles (i.e., about 25-35 days difference), AND that the subject so states on the form filled out by the subject. A difference in days outside the range of 25 to 35 days could legitimately occur, but if the gap is not within 25-35 days, ask [name] to investigate.
2. Indicate date of receipt of samples on the Sample Collection Form.
3. Obtain a ACDC Aliquot Kit. Transfer the LG Bag Label to the Sample Collection Form in the space below the Subject ID, Date, and Time.
4. Invert repeatedly to ensure homogeneity.
5. Carefully harvest the urine from the 30 mL "A or #1" vial and pipet 10 mL into one yellow-top polypropylene 10 mL tube labeled with the predetermined randomization number. Tube will also be labeled "Biologic research specimen. Human urine."
6. Cap and place the 10 mL vial in its corresponding numbered box.
7. Repeat steps 4-6 for the 30 mL "B or #2" vial.
8. Write the date, time and the technologist's initials on the Sample Collection Form. Also include the tube numbers, volume and number of tubes.

CONFIDENTIAL

9. Place the box containing the 30 mL vial and the randomized yellow-top tubes into the room temperature ACDC storage cabinet.
10. File the Sample Collection Form in the ACDC sample binder.

Quality assurance (QA):

Under the direction of the study statistician, at other times, samples may be aliquoted from the 30 mL vials and given randomization numbers (or facsimiles thereof) by following steps 4-6 above. Such specimens will come from subjects' consecutive cycles but may not necessarily be paired in the same way as the principal samples. For example, if previous randomized samples were from Subject X in months 1&2 and 3&4, then QA could include sending samples from Subject X's months 2&3 and/or repeat samples from the original months such as 3&4. Such QA may be performed and analyzed at interim stages of the protocol only if it does not break the blind of the principal study. Repeated failure to be in conformation with the hypothesis during QA may result in early termination of the study, if the statistician and principal investigator agree.

Shipping of samples:

When sufficient samples are obtained, the 10 mL yellow-top tubes labeled "Biologic research specimen. Human urine." with random numbers affixed AND NO OTHER INFORMATION AFFIXED (specifically excluded is any information that could in any way identify the participating subject by name, birthdate, or any other identifying information) will be sent (by mail or other approved delivery method) for processing to Urobiologics LLC, [name]. THE GREEN-TOP VIALS THAT SUBJECTS USED FOR THEIR COLLECTION OF URINE MUST REMAIN LOCKED IN THE C.L.A.S.S. LABORATORY AND MAY NOT BE SHIPPED OUT (because they may contain identifying information about the subjects or might otherwise "break the blind").

WHEN THE SUBJECT BELIEVES THAT SHE WILL LIKELY SHIP HER SPECIMENS BACK AND NOT RETURN SAMPLES IN PERSON, THE STUDY WILL PROVIDE THE APPROPRIATE MATERIALS TO SHIP THE SPECIMEN THAT COMPLY WITH ALL DOT REGULATIONS. THE STUDY WILL PROVIDE THE TRIPLE PACKAGING (1- VIAL, 2 SEALED BAG, 3- ENVELOPE) RETURN ENVELOPES WITH PREPAID RETURN SHIPPING LABEL. THESE URINE SAMPLES ARE CONSIDERED INFECTIOUS SUBSTANCES CATEGORY B (SEE NOTE BELOW), THEREFORE TO COMPLY WITH DOT REGULATIONS THE SAMPLE MUST CONTAIN THE TEXT: "EXEMPT HUMAN SPECIMEN" WHICH MUST BE VISIBLE ON OUTSIDE OF ENVELOPE. THIS EXEMPT STATUS IS FOR SPECIMEN SHIPPING ONLY AND DOES NOT IMPLY ANY IRB EXEMPTION.

URINE IS CONSIDERED UNDER INFECTIOUS SUBSTANCES CATEGORY B

MATERIALS THAT ARE INFECTIOUS BUT DO NOT MEET THE CRITERIA FOR INCLUSION IN CATEGORY A
ASSIGNED TO UN 3373 (CATEGORY B, INFECTIOUS SUBSTANCES)
HUMAN OR ANIMAL MATERIAL TRANSPORTED FOR RESEARCH, DIAGNOSIS, DISEASE TREATMENT, ETC.

PATIENT SPECIMENS FOR WHICH THERE IS MINIMAL LIKELIHOOD THAT PATHOGENS ARE PRESENT AND ARE TRANSPORTED IN A PACKAGING WHICH

CONFIDENTIAL

WILL PREVENT ANY LEAKAGE ARE CONSIDERED “EXEMPT HUMAN SPECIMEN” OR “EXEMPT ANIMAL SPECIMEN”.

THEY MUST BE LABELED AS “EXEMPT HUMAN/ANIMAL SPECIMEN”.
THEY MUST USE TRIPLE PACKAGING SYSTEM.

Processing of samples in Urobiologics laboratory:

Urine samples are processed to remove non-hormonal redox compounds and then reacted with a redox indicator to evaluate each sample in the pair of urines as an oxidative or a reductive reaction.

Results are reported to the UM C.L.A.S.S. Laboratory according to the randomized numbers provided with the samples.

At the conclusion of the study the residual de-identified urine will be shipped to the Sponsor. Upon completion of processing, the sponsor will destroy all remaining materials and verify the destruction and disposition to the class laboratory.

Statistical power analysis and planned stat analysis:

From each experimental subject, we will have three non-overlapping pairs of consecutive urine samples taken. For each sample pair a blinded determination will be made by Urobiologics as to which sample in the pair was reductive. For the sake of simplicity, consider the case where these samples are collected in 6 consecutive months. Let “A” be the event that the reductive sample in the pair corresponds to the earlier cycle and “B” its converse. Then, the hypothesis of alternating reductive cycles is supported if the sequences AAA or BBB are over-represented relative to others. To analyze this, we will map whether the 2nd and 3rd pairs are successfully determined conditional

CONFIDENTIAL

on the first. Let “Y” denote success and “N” denote failure. Each subject then has one of the four patterns: YY, YN, NY, NN representing whether the 2nd and 3rd paired cycles are correctly predicted by the alternating cycle hypothesis. The hypothesis is supported by over-representation of YY relative to chance if predictions were made under the null of $P(Y) = 0.5$ with successive pairs called independently.

Consequently, we will first use a chi-squared goodness of fit test to evaluate the hypothesis below at the $\alpha=0.01$ level:

$H_0: p = 0.5$

and $P(YY) = p*p$; $P(YN) = P(NY) = p*(1-p)$; $P(NN) = (1-p)*(1-p)$.

Under the alternative that $p = 0.75$, 37 subjects are needed to give 90% power to reject the null hypothesis at a significance level of 0.01. Assuming that <10% of enrolled subjects will be lost to attrition, we need to enroll a minimum of 40 subjects to achieve the target sample size.

Subsequently, we will estimate “p” in the model above using the total proportion of “Y” and form a confidence interval for this estimate using a bootstrap procedure to account for the pairing of samples within women. As a secondary analysis, we will use a likelihood ratio test to evaluate the validity of the independence assumption by comparing the one-parameter independence model to the four-parameter model with unique cell probabilities. Finally, for exploratory analyses to generate future hypotheses we will fit a mixed logistic regression in which the log odds of outcome “Y” are expressed as a linear function of any covariates to be explored and a random intercept inducing correlation between repeated measures within each woman.

Study Flow Chart

Study Procedure	Screening	Cycle 1	Cycle 2	Cycle 3	Cycle 4	Cycle 5	Cycle 6	All samples processed
Informed Consent	X							
Inclusion/Exclusion form	X							
Medical History/ Demographics	X							
Assign a Subject Number	X							

Give three urine collection kits to subject.
 
Each kit will contain two units. The two units provide for two collections about a month apart for each kit. Each unit will have one cup, one green-cap vial, one dropper, one instruction sheet, and one form to fill out with period start date and dates of collection of sample along with other relevant queries and instructions for returning the samples.
 
When the subject believes THAT she will likely ship her specimens back and not return samples in person, THE STUDY WILL PROVIDE THE APPROPRIATE MATERIALS TO SHIP THE SPECIMEN THAT COMPLY WITH ALL D.O.T. REGULATIONS. THE STUDY WILL PROVIDE THE TRIPLE PACKAGING (1- VIAL, 2 SEALED BAG, 3- ENVELOPE) RETURN ENVELOPES WITH PREPAID RETURN SHIPPING LABEL. THESE URINE SAMPLES ARE CONSIDERED INFECTIOUS SUBSTANCES CATEGORY B (SEE NOTE BELOW), THEREFORE TO COMPLY WITH D.O.T. REGULATIONS THE SAMPLE MUST CONTAIN THE TEXT: "EXEMPT HUMAN SPECIMEN" WHICH MUST BE VISIBLE ON OUTSIDE OF ENVELOPE. THIS EXEMPT STATUS IS FOR SPECIMEN SHIPPING ONLY AND DOES NOT IMPLY ANY IRB EXEMPTION.
	X*							
Determine if subject accepts reminders	X							
Remind subjects at least twice in each cycle (when and as agreed by subject)		X	X	X	X	X	x	

CONFIDENTIAL

Receive urine samples, process in CLASS Lab per protocol.			X		X		X	
Send urine samples to Urobiologics			IN BATCHES OF SAMPLES					
Code data from Urobiologics			AS SAMPLES ARE REPORTED					
Quality assurance per protocol			AS SAMPLES ARE AVAILABLE					
Break blind; statistical analysis								X

*At any time, provide more kits if needed.

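### Does the QA example's use of month pairs that share a vial disable the early-termination check?

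*Combined protocol and SAP*

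**What the plan says.** The Quality assurance (QA) section lets the study statistician direct that further aliquots be drawn from the retained 30 mL vials. The pairs come from consecutive cycles but need not match the principal pairing. As an illustration, for a woman whose months 1&2 and 3&4 have already been sent, "QA could include sending samples from Subject X's months 2&3 and/or repeat samples from the original months such as 3&4". Interim QA is allowed "only if it does not break the blind of the principal study". The consequence is stated as "Repeated failure to be in conformation with the hypothesis during QA may result in early termination of the study, if the statistician and principal investigator" concur. The section gives no comparator for a QA pair, no chance level, no number of pairs and no count that makes failure repeated.

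The chance level of 0.5 appears only in Statistical power analysis and planned stat analysis, for the principal data: "we will have three non-overlapping pairs of consecutive urine samples taken", each yielding a blinded determination "as to which sample in the pair was reductive", with the null of P(Y) = 0.5 "with successive pairs called independently". The Study design synopsis leaves unblinding to the end: "When all samples have been collected and analyzed, the blind will be broken". The Study Flow Chart row "Receive urine samples, process in CLASS Lab per protocol" is marked at cycles 2, 4 and 6.

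**The concern.** A call is relative within a pair, so one pair alone cannot show alternation. It has to be compared with another pair from the same woman. With only months 1 to 4 in hand, 2&3 can be compared only with 1&2, with 3&4, or with repeats of them, and each shares a vial with it.

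Sharing a vial builds in agreement with the hypothesis. If month 2 happens to be high, it tends to exceed both month 1 and month 3, and that reads as a reversal. Conformity by chance then exceeds 1/2. A repeat of the same pair is a stronger case: with a repeatable assay it agrees with its first call whether or not cycles alternate. If QA results were read against 1/2, a failing hypothesis could look acceptable, and the early-stop provision would lose much of its use. Scoring 2&3 also needs a neighbouring call in cycle order, which sits awkwardly with keeping the blind to the end.

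**Working it through.** **Inputs.** From the statistical section: p = 0.5 under the null, p = 0.75 under the alternative, alpha 0.01, 37 subjects, 90% power. From the QA section: pairs 1&2, 2&3 and 3&4. Assumed, because the plan gives none: 20 women with one QA pair each, and the bounds used below.

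**The plan's own figure.** At p = 0.75 the four cells are 0.5625, 0.1875, 0.1875 and 0.0625. The effect size is w² = (0.3125² + 2 × 0.0625² + 0.1875²)/0.25 = 0.5625. The noncentral chi-square with 3 df reaches 90% at n = 35. Exact enumeration reaches it at n = 36 (90.3%) and gives 91.0% at n = 37. The stated 37 is sound.

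**One neighbour, no alternation.** Of the 6 orderings of three exchangeable, untied monthly levels, 4 have month 2 as a peak or trough. Conformity is 4/6 = 0.667 and failure 1/3. For 1&2 against 3&4 (no shared vial) it is 12/24 = 0.5.

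The 2/3 is the highest value among the models tried:
- Assay noise: if repeats agree with probability r, let x = sin((r − 0.5)π). Conformity is 0.5 + arcsin(x/2)/π, which is 0.658 at r = 0.9, 0.633 at r = 0.8 and 0.5 at r = 0.5.
- Cycle-to-cycle correlation 0.5: 0.58.
- A 50:50 binary status with ties broken at random: 0.625.

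**Both neighbours, no alternation.** Alternation predicts that 2&3 reverses against 1&2 and against 3&4. This holds in 10 of 24 orderings, so failure is 14/24 = 0.583.

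**At p = 0.75.** Let q be the probability that a call matches the alternation. From q² + (1 − q)² = 0.75, q = 0.8536. With perfect repeats, calls on adjacent pairs have correlation 0.5. A bivariate normal gives conformity with one neighbour of 0.819 (failure 0.181). A trivariate normal, with correlation 0 between 1&2 and 3&4, gives conformity with both of 0.694 (failure 0.306).

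**Chance of meeting a bound among 20 women (binomial, perfect repeats).**

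| Scoring | Bound on failures | No alternation | p = 0.75 |
|---|---|---|---|
| 2&3 v one neighbour | 11 | 3.8% | under 0.1% |
| 2&3 v one neighbour | 7 | 52% | 5.6% |
| 2&3 v both neighbours | 11 | 70% | 2.0% |
| 2&3 v both neighbours | 12 | 53.5% | 0.6% |
| 2&3 v 4&5, no shared vial | 11 | 41% | 0.4% |

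The failure rates used are, row by row, 1/3 v 0.181 (twice), 0.583 v 0.306 (twice) and 0.5 v 0.25.

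**Sensitivity to noise.** If all noise is per aliquot, calls are independent. Failure against both neighbours is then 0.75 without alternation and 1 − q³ − (1 − q)³ = 0.375 at p = 0.75. A bound of 14 is met in 79% and 0.3% of trials. The right bound moves with repeatability, but the contrast remains.

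**Effect on the final test.** The stop is for failure only, so it cannot raise type I error. If a bound of 12 on both neighbours were always obeyed, and every stopped trial would otherwise have rejected, power at 37 subjects is at least 0.910 − 0.006 = 0.904. A bound of 11 gives 0.910 − 0.020 = 0.890 on the same worst-case reckoning, and the plan leaves the decision to judgement.

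**The case for a change.** The strongest case for a change is that the overlap is real and the section is silent on it. Scored against one neighbour with a majority rule, the check would stop only 3.8% of trials without alternation, against 41% if chance were 1/2. Lower counts point the same way: with 10 women, at least 5 failures occur in 21% against 62%. Repeats sit under the same trigger although they say nothing about alternation. A few sentences naming 2&3 against 4&5, a number and a bound would settle all of this and would decode no principal call.

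Part of this stands. QA conformity on vial-sharing pairs should not be read against 1/2, repeats measure assay repeatability, and the comparator, the count and the handling of the blind are unstated.

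The claim that failure would seldom be seen does not stand. It depends on scoring against one neighbour only and on a majority rule, neither of which is in the plan. With the same single neighbour, 7 or more of 20 fail in 52% of trials without alternation. Comparing 2&3 with 4&5 is already permitted, since the example only illustrates. It also has a price: month 5 arrives with the third kit, so each woman is checked after cycle 6 instead of cycle 4, and only women whose cycles 2 to 5 are consecutive contribute. The blind condition is itself a safeguard: a comparison that would break it may not be made. Re-randomised repeats of the neighbouring pairs, which the example already mentions, are one possible comparator.

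**Conclusion.** The arithmetic behind the worry is correct, but it does not show a defect that needs a change. Chance conformity with one vial-sharing neighbour is at most 2/3 in the models examined. The plan never says that such a pair is to be read against 1/2, or against one neighbour only. Used in full, the plan's example discriminates at least as well as the non-overlapping alternative (53.5% v 0.6% at a bound of 12, compared with 41% v 0.4% at a bound of 11), and two cycles sooner for each woman.

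What remains is missing detail in a discretionary check. The study statistician directs it, and stopping needs that person and the principal investigator to agree. A statistician scoring 2&3 would allow for the shared vial and keep repeats apart as a repeatability measure. The final test uses non-overlapping pairs and its type I error is untouched; the stated power is not materially at risk.

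These figures assume exchangeable, untied levels without alternation, normal levels at p = 0.75, and 20 women. The documents give no assay repeatability, so any bound would have to be set with that in view.

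### The QA check is judged by conformity with the study hypothesis, not by agreement between repeat readings, so a QA stop cannot be read as an assay failure and has an unstated power cost

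*Combined protocol and SAP*

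**What the plan says.** The Quality assurance (QA) section of the combined protocol and SAP allows further aliquots to be drawn from the stored vials, under the study statistician's direction, and sent under random numbers. On the material it says: "QA could include sending samples from Subject X's months 2&3 and/or repeat samples from the original months such as 3&4". On timing and masking it says: "QA may be performed and analyzed at interim stages of the protocol only if it does not break the blind of the principal study". The Study Flow Chart schedules QA "AS SAMPLES ARE AVAILABLE".

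The one stated consequence is: "Repeated failure to be in conformation with the hypothesis during QA may result in early termination of the study", with the condition "if the statistician and principal investigator agree". The section gives no number of QA pairs, no definition of repeated failure, no measure of agreement between repeat calls and no reliability threshold.

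The section on statistical power and planned analysis scores each woman's second and third pairs Y or N, "representing whether the 2nd and 3rd paired cycles are correctly predicted by the alternating cycle hypothesis". The primary test is a chi-squared goodness-of-fit test of p = 0.5 at the 0.01 level, with 37 women for 90% power at p = 0.75 and 40 enrolled. That section mentions neither the QA reading nor the possible stop. The Study design synopsis places unblinding after all samples have been collected and analysed, and the flow chart agrees.

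**The concern.** A quality check should show whether the laboratory can be relied on, whatever the biology turns out to be. This one is passed when the hypothesis looks true and failed when it looks false. A sound assay in women who do not alternate would fail, and a poor assay could pass by chance.

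Two things are at stake. First, a true negative answer could be labelled a quality failure and end the study before 37 women are evaluable, and the stated power takes no account of that. Second, if the study stops, or finishes with p near 0.5 or at an intermediate value, no pre-specified analysis shows whether the assay or the biology is responsible. The synopsis calls this a validation study, so that is a question it should be able to answer.

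**Working it through.** 1. **The plan's own figure.** Inputs from the planned analysis: p = 0.75, alpha 0.01, four cells, fully specified null (3 degrees of freedom).
   - Cell probabilities are 0.5625, 0.1875, 0.1875 and 0.0625, against 0.25 each.
   - w² = (0.3125² + 2 × 0.0625² + 0.1875²)/0.25 = 0.5625. The critical value is 11.345.
   - The noncentral chi-squared formula gives a minimum of 35 women, and 92.7% power at 37.
   - Simulating the multinomial (400,000 runs) at 37 gives 91.0% power and size 0.0087.
   - The plan's 37 is therefore sound when there is no early stop.

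2. **What conformity measures, non-overlapping pairs.** Let a be the probability that a pair is called in its true order. Let q be the probability that two non-overlapping pairs from one woman truly have the same order. Assume that call errors are independent. Then:
   - repeat agreement r = a² + (1 − a)²
   - conformity = q·r + (1 − q)(1 − r)

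| Case (assumed values) | a | q | Conformity | Repeat agreement |
|---|---|---|---|---|
| Perfect assay, no alternation | 1 | 0.5 | 0.50 | 1.00 |
| Coin-flip assay, perfect alternation | 0.5 | 1 | 0.50 | 0.50 |
| Perfect assay, imperfect alternation | 1 | 0.75 | 0.75 | 1.00 |
| Imperfect assay, perfect alternation | 0.854 | 1 | 0.75 | 0.75 |

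   Conformity gives the same value within the first two rows and within the last two. Agreement separates both.

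3. **Overlapping pairs (months 2&3).** Assume independent cycle values, no alternation and perfect ranking. Three cycles have 6 equally likely orders, and in 4 of them months 2&3 run opposite to months 1&2. Conformity is then 4/6 = 2/3, against 1/2 for a coin-flip assay. If 1&2 and 3&4 already agree, it is 5/6. Here the two explanations differ somewhat, but 0.5 is not the chance level and the plan sets no other benchmark.

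4. **Effect of a stop.** The plan states no rule. Assume a stop when no more than half of the QA calls conform, with those calls being the first primary Y/N calls (two per woman) and independent as in the plan's model.

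| QA calls | Stops at p = 0.75 | Power at 37 (91.0% without stop) | Stops at p = 0.5 |
|---|---|---|---|
| 6 | 16.9% | 77.0% | 65.6% |
| 10 | 7.8% | 85.1% | 62.3% |
| 20 | 1.4% | 90.3% | 58.8% |

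   The power loss is 14.0, 5.9 or 0.7 percentage points. Type I error falls from about 0.0087 to between 0.003 and 0.004.

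5. **What an agreement rule could do.** Take 20 repeat pairs and an assumed cut of at least 16 agreeing. A coin-flip assay (r = 0.5) passes 0.6% of the time. A 95%-accurate assay (r = 0.95² + 0.05² = 0.905) passes 96% of the time.

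**The case against.** The strongest reply is that this is an optional, discretionary futility stop, which a sponsor may legitimately want. It needs two roles to agree and acts only on failure. Repeats are already permitted ("repeat samples from the original months such as 3&4"), so agreement could be computed after unblinding. That is fair as far as it goes. But the stop is presented as QA, no agreement analysis is pre-specified, and repeats are only one optional form of QA.

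A reader might draw four stronger conclusions that the documents do not support.

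- **That QA breaks the blind.** The masking described is chiefly that of the sponsor's laboratory. No section says that the statistician is masked to cycle order, and interim QA is allowed "only if it does not break the blind of the principal study". What stands is a tension. Judging conformity means linking calls to subject and cycle order, usually against the woman's other pairs, while the synopsis delays unblinding to the end. The plan does not say how both can hold.
- **That QA re-examines the primary outcome data.** QA reads fresh aliquots, and months 2&3 are not a principal pair in the plan's example. It is a look at the primary hypothesis, not necessarily at the stored primary calls.
- **That type I error is inflated.** A stop for non-conformity alone lowers it.
- **That conformity can never separate assay from biology.** This is exact only for non-overlapping pairs (step 3).

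Agreement also has limits. It shows reliability, not that the assay reads hormonal redox status. Vials are kept at room temperature, so a late repeat could disagree because of storage.

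**Conclusion.** The concern holds in this form: the only stated QA criterion is conformity with the hypothesis under test, and repeated failure on it may end the study without any account in the power calculation. It is more than a missing detail, because the rule as written treats a true negative as a quality failure.

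The equal 0.50 conformity in the two opposite cases follows from the definitions and from independent call errors. The 2/3 figure rests on independent, perfectly ranked cycle values. The size of the power loss cannot be taken from the documents. Under the assumed rule it runs from 14 points with 6 calls to under 1 point with 20, so neither a large nor a negligible loss should be claimed. The plan should be changed before QA readings are used for any decision.

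**What to change.** In the QA section:

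- Define the QA measure as agreement between the original and the repeat call on the same pair. Send repeats under new random numbers and have the CLASS Laboratory match them by tube number, without using cycle order.
- Pre-specify the number of repeat pairs and the threshold. The 20-pair rule with at least 16 agreeing is one example.
- Draw repeats close in time to the originals, so that storage is not mistaken for assay error.
- Base any QA-driven termination on low agreement, and report agreement beside p.
- Remove conformity with the hypothesis as a QA stopping ground. If the sponsor wants to stop early for lack of alternation, specify this separately as a futility look, with its timing, its rule and its power cost. Say who sees cycle order.
- Hold QA results that bear on alternation, such as months 2&3, until the blind is broken, unless they belong to that futility look.

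The cost is mainly wording. Repeat aliquots are already allowed, and a full 30 mL vial leaves 30 − 10 = 20 mL after the first aliquot. The small downside is losing the informal option to stop early.
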